10.3 Subject Withdrawal

Study subject may be withdrawn or terminated for the following reasons:

- Subject death

- Concomitant disease or any pre-existing disease or condition that precludes subject's participation.
- Subject voluntarily chooses not to participate further in the study.
- Subject's non-compliance with study procedures.
- Lost to follow-up: the subject has missed a study visit and three documented attempts to contact the subject are unsuccessful. A subject who misses a study visit should be contacted by site personnel to determine the reason for the missed visit, which should be documented in the subject's study records. Note: A subject who misses a study visit but attends a subsequent visit will no longer be considered lost to follow-up.
- In the clinical investigator's opinion, a significant safety concern arises that requires subject discontinuation.
- In the clinical investigator's opinion, it is not in the best interest of the subject to continue study participation.
- In the sponsor's or IRB's opinion, it is not in the best interest of subject to continue the study.

If a subject decides to withdraw from the study, clinical investigator should follow patients with ongoing AEs till resolution according to the standard of care. Data collected up to the point of subject withdrawal or termination will be maintained in the study database and included in analyses as appropriate.

All enrolled subjects, including those withdrawn or lost to follow-up, will be accounted for and documented.

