11.2 Baseline/Procedure Phase

Baseline assessment

Upon meeting eligibility requirements, subjects in both cohorts will undergo a baseline endoscopic examination, including grading and video recording.

Female subjects of childbearing potential will undergo a urine pregnancy test prior to the baseline procedure and be required to use acceptable contraceptive method(s) during the entire duration of the study follow-up. Acceptable methods of contraception may include:

Established use of oral, injection or implantable hormonal contraceptives;

- Double-barrier methods (i.e., intra-uterine devices) and barrier contraceptives (i.e., condom, diaphragm or cervical/vault caps) used with spermicide (foam, gel, film, cream or suppository);

- Female sterilization (e.g., tubal occlusion, hysterectomy or bilateral salpingectomy); or
- Vasectomized male partner, if the sole partner for the subject.

Note: The baseline endoscopic assessment and pregnancy testing must be performed before the dilation procedure.

PK cohort: Baseline assessment will also include:

- SNOT-22 questionnaire.
- A blood sample collection prior to the baseline procedure.
- Instructions for urine sample collection through 24 hours after the baseline procedure
 - Urine collection starting with the void after the procedure through 24 hours on following day.

Subject preparation for baseline procedure

Subjects will be prepared for the baseline procedure per investigator's standard protocol used for nasal endoscopy. The topical anesthesia regimen may consist of:

- Spraying the nasal cavity with 4% lidocaine (or equivalent, such as pontocaine) with oxymetazoline (or equivalent) nasal decongestant spray;
- Placing cotton pledges soaked in lidocaine (or equivalent) and oxymetazoline (or equivalent) solution against the inferior turbinate, and into the ethmoid sinus (if available in the clinic setting, topical cocaine may be used); and
- Injecting into the sinus tissue and/or polypoid tissue with lidocaine (or equivalent) as necessary.

The anesthesia period should be as long as necessary to ensure complete numbness of the subject's septum and middle turbinate. Once properly anesthetized, subjects may undergo the baseline procedure.

Baseline procedure

All UP Devices will be provided by the study sponsor and must be used according to the instructions for use (IFU). Subjects will undergo bilateral in-office dilation of the FSO with the study UP Device.

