16.8 Analysis Populations

PK cohort: The PK population will consist of all subjects in the safety population with at least one non-missing and eligible plasma concentration value.

Safety population will consist of all subjects and sinuses exposed to investigational device with successful dilation of at least one FSO.

Randomized cohort: All primary analyses will be conducted on the intent-to-treat population. Additional analyses may be performed on the per-treatment-evaluable population.

- *Intent-to-Treat* (ITT) population will consist of all subjects and sinuses where a sinus dilation was attempted. An attempt occurs when the physician introduces the UP Device into the subject's nostril with the intent of dilation. Subjects and sinuses will be analyzed according to randomization assignment.
- *Per-Treatment-Evaluable* (PTE) population will consist of all randomized patients and sinuses which have received the assigned study device in the target sinus, who have no major procedural protocol deviations, and for whom follow-up data are available.

If a subject decides to discontinue from the study, every attempt will be made to continue to collect the safety and efficacy data according to the protocol procedures.

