9.3.2 Randomized Cohort

The primary and secondary efficacy endpoints that are continuous variables will be analyzed using paired t-test. All statistical tests will be two-sided and interpreted at a 5% significance level. A

p-value < 0.05 will be considered statistically significant. Unless stated otherwise, a two-sided 95% CI will be calculated and presented.

Categorical variables will be analyzed using McNemar's test for correlated proportions. In this intra-patient control study design, only discordant pairs of observations contribute to evidence of treatment effect. The appropriate test is an exact binomial calculation, using a 2-sided alpha of 0.05 or a 1-sided alpha of 0.025. In addition, frequency distributions showing findings by treatment side will be presented with counts, percentages and, where appropriate, exact 95% CI using the Clopper and Pearson method.

All available data at each time point will be presented. No imputations for missing data are planned, unless indicated otherwise. For the primary efficacy endpoint, if missing values exceed 10%, sensitivity analyses with imputations will be conducted. (see [Section 10.3.2.2](#)).

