9.4.2 Randomized Cohort

The sample size was calculated based on the difference in the patency grade at Day 30 between the treatment and control sides with the following assumptions:

- Expected mean difference of 0.5 between the treatment and control sides in patency grade
- A SD of 1.1 for side-to-side difference in the patency grade of the FSO
- Target power of $\geq 90\%$
- Type I error rate of $\alpha = 0.05$, 2-sided

A mean difference in patency grade of 0.5 between the treatment and control sides favoring treatment sides was considered clinically meaningful. Based on standard formulas for a paired t-test, a sample size of 53 subjects provides at least 90% power to detect a difference of 0.5 in mean patency grade between treatment sides. Assuming up to 25% of subjects with non-evaluable data on one or both sides, additional 17 subjects will be enrolled for a total of 70 subjects in the randomized cohort.

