10.3.2 Randomized Cohort – Primary Efficacy Endpoint

The primary efficacy endpoint is the difference in patency grade of the FSO between the treatment and control sides at Day 30 as determined by an independent, blinded sinus surgeon based on the centralized video-endoscopy review. Patency of the FSO will be assessed endoscopically by probing with a 3-mm olive-shaped frontal sinus suction tip (“suction tip”) and will be analyzed using the paired t-test.

For each subject, the difference in patency grade of the FSO between the treatment and control sides will be calculated and then averaged across all subjects. The difference in patency grade for a given subject will be set as missing if one of the FSO is unable to be viewed or graded.

The primary efficacy hypothesis is that mometasone furoate (MF) from the UP Drug-Coated Device will significantly increase the patency grade on the treatment side compared to control. The statistical test will be paired t-test where the difference in patency grade between treatment and control sides is determined.

The relevant null and alternative hypotheses for this primary efficacy endpoint are:

- $H_0: \mu = 0$
- $H_1: \mu \neq 0$

where μ is the mean difference in the FSO patency grade between the treatment and control sides at Day 30. The study will be considered successful if there is a statistically significant difference in the mean patency grade in favor of the UP Drug-Coated Device.

Although the alternative hypothesis is specified as two-sided, only a statistically significant difference in patency grade favoring treatment sides will constitute evidence of effectiveness. The two-sided α for this test is 0.05 (or one-sided α of 0.025).

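### Protocol 10.3 permits withdrawal for non-compliance after a one-time treatment, and no passage promises Day 30 or Day 60 data for subjects the site or sponsor withdraws

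*Protocol*

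**What the plan says.** Protocol 10.3 gives a list of reasons for which a subject may be withdrawn or terminated. One is "non-compliance with study procedures". Others on the list are also decisions of the investigator, sponsor or IRB and not of the subject.

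On data, the same section says: "Data collected up to the point of subject withdrawal or termination will be maintained in the study database and included in analyses as appropriate". It adds that a subject who decides to withdraw with an ongoing adverse event should be followed to resolution under standard of care.

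Protocol 16.8 says: "If a subject decides to discontinue from the study, every attempt will be made to continue to collect the safety and efficacy data".

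Treatment is a single event. Protocol 11.2 states: "Subjects will undergo bilateral in-office dilation of the FSO with the study UP Device". There is no repeat dosing.

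The primary parameter is defined in SAP 10.3.2: "where μ is the mean difference in the FSO patency grade between the treatment and control sides at Day 30". The intent-to-treat population is the principal one (SAP 7.2.1). A subject's difference is missing if either side cannot be graded (SAP 10.3.2), and SAP 9.3.2 plans no imputation in the main analysis.

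**The concern.** In a trial of continuing medication, withdrawing a non-compliant subject at least stops exposure. Here exposure is complete on Day 0, so later withdrawal removes only the outcome.

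As drafted, the text also promises more follow-up for subjects who choose to leave than for those the site removes. Someone willing to attend on Day 30 could be withdrawn for a breach, with no stated obligation to record the endoscopy.

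Two things are at stake. First, each such withdrawal before Day 30 takes a pair out of the primary analysis. Some breaches may be related to how the sinuses are doing. One example is steroid use outside the permitted conditions, such as an intranasal spray started before the Day 14 visit by a subject with recurring symptoms. Second, adverse events are to be collected through Day 60, and new events after such a withdrawal could go unrecorded.

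**Working it through.** **1. Who is promised continued follow-up**

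| Situation | Data before withdrawal | Continued efficacy data | Follow-up of ongoing adverse events |
|---|---|---|---|
| Subject decides to leave | Kept (10.3) | Every attempt made (16.8) | To resolution (10.3, 14.3) |
| Investigator or sponsor withdraws the subject | Kept (10.3) | Not addressed | Not expressly addressed on withdrawal |

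The second row is the gap. Section 10.3 is a rule about keeping data. It neither orders collection to stop nor requires it to continue.

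**2. The plan's own sample size**

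Inputs from SAP 9.4.2: mean difference 0.5, SD of the paired difference 1.1, two-sided α = 0.05, target power at least 90%. On the test, SAP 9.3.2 says "All statistical tests will be two-sided and interpreted at a 5% significance level". The stated result is that "a sample size of 53 subjects provides at least 90% power to detect a difference of 0.5 in mean patency grade".

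Paired t-test power uses the noncentral t distribution with n − 1 degrees of freedom and noncentrality (0.5/1.1)·√n. The smallest n reaching 0.90 is 53, with power 0.901, so the plan's figure reproduces. (Protocol 16.2 mentions a one-sided test beside the two-sided α. One-sided 0.05 would need only 43, so 53 is the two-sided figure.) The total is 53 + 17 = 70, an allowance of 17/70 = 24.3%.

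**3. Power as pairs are lost from 70**

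No document gives a rate of withdrawal for non-compliance, so this is a range.

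| Pairs lost | Pairs left | Power |
|---|---|---|
| 0 | 70 | 0.963 |
| 4 | 66 | 0.953 |
| 7 | 63 | 0.944 |
| 10 | 60 | 0.934 |
| 14 | 56 | 0.916 |
| 17 | 53 | 0.901 |

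If 5% of 70 were withdrawn this way (an assumption; 3.5, so 3 or 4 subjects), the cost is about one percentage point: 0.963 − 0.953 = 0.010.

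**4. Possible bias**

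A lost subject takes both sides out, so the sides stay balanced. Bias arises only if the lost subjects' side differences differ from those of the rest. It equals (fraction lost) × (mean among retained − mean among lost). With 4 of 70 lost, a retained mean of 0.5 and a lost mean of 0 (assumptions), this is 4/70 × 0.5 = 0.029 of a grade.

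**5. Whether the missing-data plan covers it**

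SAP 10.3.2.2 runs its analyses only when more than 10% of primary data are missing, which is 8 or more of 70. Its list of missing data does not name withdrawal, although an absent Day 30 visit would presumably count as missed. The only option there that uses observed data is the investigator's own Day 30 grade, which a subject no longer followed would not have. The remaining options assign constants.

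As an illustration of what that means, suppose the observed pairs have mean 0.5 and SD 1.1 and every missing pair is set to the worst case of 0 − 4 = −4:

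- 2 missing: mean (68 × 0.5 − 2 × 4)/70 = 0.371, t = 2.35.
- 3 missing: mean (67 × 0.5 − 3 × 4)/70 = 0.307, t = 1.82.

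The critical value is about 1.99. That analysis is extreme by design and is sensitive to a handful of missing pairs from any cause. An observed Day 30 grade is therefore worth having.

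**The case against.** A reader might infer that data collection stops at withdrawal and that the plan itself creates missing primary outcomes. The documents do not support this. Section 10.3 says what happens to data already collected and gives no instruction to stop, and withdrawal is discretionary.

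A reader might also infer that subjects who take steroids because they are doing badly are thereby non-compliant and drop out of every analysis. That is too strong as well:

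- Protocol 12 and 13.1 allow other corticosteroids when clinically necessary under stated conditions, and allow intranasal sprays after the Day 14 visit in the randomized cohort. A subject who meets those conditions is on protocol.
- The intervention sensitivity analysis (Protocol 16.7, SAP 10.3.2.1) uses the investigator's grade from the visit before the intervention, and 10.3 keeps that grade. The text describes replacing a Day 30 grade, so it is unclear how it would treat a subject who has none. Nothing excludes such a subject.

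The further objections are fair. A missed visit already triggers contact, and a subject who attends later is no longer counted as lost. Deviations are already defined in Protocol 17.2.2. The 25% allowance absorbs a few losses, and power falls below 90% only after all 17 spare pairs are gone. A subject who refuses to attend cannot be imaged whatever 10.3 says.

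What survives is the drafting gap. No passage expressly covers continued collection after a withdrawal by the investigator or sponsor, and one of the listed grounds has no treatment left to stop.

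**Conclusion.** The point holds as a cheap improvement. Protocol 10.3 permits withdrawal for non-compliance when withdrawal can only end observation, and 16.8 does not reach subjects withdrawn by the investigator or sponsor. Avoidable and possibly outcome-related loss of Day 30 pairs is therefore allowed.

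The power effect is small: about 96% with 70 pairs, about 95% with 66 and 90.1% with 53. The bias in step 4 is also small for a few subjects. These figures rest on the SAP's 0.5 and 1.1, and on an assumed number of withdrawals, since none is documented. The link between non-compliance and outcome is plausible but not shown. The main gain is completeness of the intent-to-treat analysis and of adverse event data through Day 60, and it applies only to subjects who would still attend.

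**What to change.** 1. In Protocol 10.3, state that for the randomized cohort non-compliance alone does not end follow-up. It is already recorded as a deviation under 17.2.2.
2. In Protocol 16.8, extend the continued-collection sentence to withdrawals initiated by the investigator or sponsor. Scheduled endoscopy (including the Day 14 and Day 30 videos and the Day 60 visit) and adverse event data would then still be collected unless the subject withdraws consent, dies or cannot be reached.

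The cost is protocol wording and an instruction to sites. The downside is that sites must keep following a few uncooperative subjects.

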11 SUBJECT TREATMENT AND STUDY PROCEDURES

11.1 Screening Phase

Pre-screening

During the pre-screening phase, clinical investigators or designees will perform an initial evaluation of potential candidates for study eligibility. This initial pre-screening phase may include review of existing patient information (e.g., previously performed diagnostic measures, medical history, sinus endoscopies, sinus surgery).

Consent, enrollment, and screening

If the patient appears to be a potential candidate for the study based upon existing information, written informed consent will be obtained. No protocol required testing will be performed solely for the purposes of this study prior to obtaining patient written informed consent.

Clinical investigators or designees will approach the patient to obtain written informed consent. The background of the proposed study, the dilation procedure, the follow-up schedule and all potential risks and benefits will be carefully explained to each patient. The clinical investigator or designee obtaining the informed consent shall:

- Avoid any coercion of or undue influence of patients to participate,
- Not waive or appear to waive patient's legal rights,
- Use language that is non-technical and understandable to the patient, and
- Provide ample time for the patient to consider participation.

Each patient must sign and date the informed consent form (ICF) approved by an appropriate Institutional Review Board (IRB) and the sponsor. Patients are considered enrolled in the study upon signing the IRB-approved ICF. Enrolled subjects will be assigned unique identifying codes by the Electronic Data Capture (EDC) system and entered into the study database. Upon enrollment, subjects will have a screening assessment.

The screening assessment for both cohorts will include:

- CT scan (must be performed within 30 days prior to enrollment in the PK cohort and prior to randomization in the randomized cohort),
- Endoscopic examination, grading and video recording,
- Female subjects of reproductive potential must confirm their nursing status, undergo a urine pregnancy test, and be informed about acceptable birth control methods as part of the screening assessment and again at baseline.

PK cohort subjects who pass the screening assessment will be asked to collect urine samples for a 24-hour duration prior to the baseline visit.

For the randomized cohort subjects, if the screening visit occurs on the same day as the baseline/procedure visit, all assessments will be recorded in the baseline visit forms. See **Section 5 Study Flow Diagram** and **Section 6 Schedule of Assessments**. All subjects who do not pass the screening assessment, including inability to confirm access to each FSO, will be considered as screen failures and will be terminated from the study. The reason for ineligibility will be recorded in the EDC system.

11.2 Baseline/Procedure Phase

Baseline assessment

Upon meeting eligibility requirements, subjects in both cohorts will undergo a baseline endoscopic examination, including grading and video recording.

Female subjects of childbearing potential will undergo a urine pregnancy test prior to the baseline procedure and be required to use acceptable contraceptive method(s) during the entire duration of the study follow-up. Acceptable methods of contraception may include:

Established use of oral, injection or implantable hormonal contraceptives;

- Double-barrier methods (i.e., intra-uterine devices) and barrier contraceptives (i.e., condom, diaphragm or cervical/vault caps) used with spermicide (foam, gel, film, cream or suppository);

- Female sterilization (e.g., tubal occlusion, hysterectomy or bilateral salpingectomy); or
- Vasectomized male partner, if the sole partner for the subject.

Note: The baseline endoscopic assessment and pregnancy testing must be performed before the dilation procedure.

PK cohort: Baseline assessment will also include:

- SNOT-22 questionnaire.
- A blood sample collection prior to the baseline procedure.
- Instructions for urine sample collection through 24 hours after the baseline procedure
 - Urine collection starting with the void after the procedure through 24 hours on following day.

Subject preparation for baseline procedure

Subjects will be prepared for the baseline procedure per investigator's standard protocol used for nasal endoscopy. The topical anesthesia regimen may consist of:

- Spraying the nasal cavity with 4% lidocaine (or equivalent, such as pontocaine) with oxymetazoline (or equivalent) nasal decongestant spray;
- Placing cotton pledges soaked in lidocaine (or equivalent) and oxymetazoline (or equivalent) solution against the inferior turbinate, and into the ethmoid sinus (if available in the clinic setting, topical cocaine may be used); and
- Injecting into the sinus tissue and/or polypoid tissue with lidocaine (or equivalent) as necessary.

The anesthesia period should be as long as necessary to ensure complete numbness of the subject's septum and middle turbinate. Once properly anesthetized, subjects may undergo the baseline procedure.

Baseline procedure

All UP Devices will be provided by the study sponsor and must be used according to the instructions for use (IFU). Subjects will undergo bilateral in-office dilation of the FSO with the study UP Device.

Prior to the baseline sinus dilation procedure, the FSO will be assessed under endoscopic visualization and the assessment will be recorded on the Endoscopic Scoring Form. Using a 3-mm olive-shaped frontal sinus suction tip, the patency and FSO diameter assessments will be performed. Final subject eligibility will be confirmed based on bilateral stenosis of the FSO on endoscopic assessment. NOTE: Physician may use light-assisted or image-guided instrument such as a smaller diameter frontal sinus seeker tip to confirm access of each FSO and if the sinus is amenable to balloon insertion.

No other devices, spacer, or packing (with or without steroid) may be used during or after the baseline dilation procedure. Aggressive suction and irrigations of the treated site should be avoided, as much as possible.

In subjects in the PK cohort, dilation of the maxillary and/or sphenoid sinus with the same UP Device may be performed, if clinically necessary, after the index dilation procedure. In subjects in the randomized cohort, dilation of the maxillary and/or sphenoid sinus with a commercially available balloon sinuplasty device may be performed, if clinically necessary, prior to randomization. No other surgical procedures at baseline will be allowed.

The steps to be followed for the in-office dilation procedure for this study are as follows:

1. Insert a compatible lightwire through the proximal end of the UP Device.
2. Insert the UP Device into the compatible sinus guide catheter.
 - a. If desired, attach the compatible sinus guide catheter handle to the sinus guide catheter before insertion of the UP Device.
3. Insert the sinus guide catheter into the FSO and position the sinus guide catheter tip opening toward the FSO (See **Section 7.2 Investigational Device** for compatible accessory devices).
4. Confirm that the lightwire is in the sinus, then advance the UP Device through the guide catheter and position it in the targeted FSO. Note: Under endoscopic visualization, ensure that the proximal end of the balloon (yellow single-band marker) is visible outside of the frontal sinus ostium.
5. Inflate the balloon of the UP Device with the compatible inflation device to 12 atmospheres (atm).
6. Hold the inflated balloon at 12 atm for a minimum of ~10 s and maximum of ~30 s.
7. Deflate the balloon.
8. Reposition the balloon distal to the first inflation site such that the proximal half of the balloon is in contact with sinus mucosa, adjacent to the first inflation site.
9. Repeat steps 5 and 6 to dilate the sinus ostium for a total of 2 inflations in each sinus ostium.
10. Retract the deflated balloon into the guide catheter before removing the dilation system out of the nostril (Note: Do not retract the tip of the UP Device beyond the blue tip marker on the guide catheter to prevent loss of the drug).

PK cohort: Subjects will undergo in-office bilateral sinus dilation with the UP Drug-Coated Device in the frontal sinuses with 2 inflations per sinus (total of 4 inflations per Device).

- Repeat steps 1 through 10 for each FSO with the same UP Drug-Coated Device. Note: Dilation of the maxillary and/or sphenoid sinus with the same UP Device may be performed, if clinically necessary. However, dilation of the maxillary and/or sphenoid sinuses must be performed only after dilation of the frontal sinuses.
- On the day of the baseline procedure, 4 additional blood draws (~ 11 ml at each timepoint) will be performed at 0.5 (\pm 5 min), 1 (\pm 5 min), 2 (\pm 10 min) and 4 (\pm 15 min)

hours following the end of the baseline procedure, defined as removal of UP Device from the nostril after successful dilation of both FSO in each subject.

Randomized cohort: Subjects will undergo an in-office sinus dilation with the UP Drug-Coated Device of the FSO randomized to treatment (2 inflations per device) while the contralateral FSO will serve as control and undergo sinus dilation with a UP Control Device (2 inflations per device).

- Steps 1 through 10 will be followed with each frontal side dilated with the assigned UP Device.

Postoperative care

PK cohort subjects will be required to collect urine samples for 24 hours following the baseline procedure.

After the baseline procedure, subjects in the PK cohort will be allowed and subjects in the randomized cohort will be required to use saline sprays/rinses/irrigations starting Day 2.

PK cohort subjects will not be allowed to use INCS sprays throughout the 30 days follow-up duration. Randomized cohort subjects will be allowed to use INCS sprays starting after the scheduled Day 14 study visit, if medically necessary.

Device disposal

The investigational and compatible accessory devices must be disposed per standard institutional practices for biohazard waste. If the UP Device or other compatible accessory devices are associated with a device-related AE, malfunction, or failure, all the components should be returned to the sponsor for evaluation, as much as possible. For the return of biohazard product, the sponsor must be contacted prior to product return for handling instructions.

Device malfunction and use error

All potential and suspected device malfunctions and use errors of the investigational device will be reported to and reviewed by the sponsor. Any AEs associated with the investigational device and/or compatible accessory devices will be recorded in the corresponding CRFs in the EDC system.

